### **Study Outcomes:**

#### **Primary outcome measures:**

- **Aim 1 – Circadian Misalignment of central clock:** Phase Angle will be measured as the difference between circadian clock (dim light melatonin onset) and behavior cycle (sleep onset)
- **Aim 2 – Barrier Function:** Mayo Endoscopic Score and Intestinal permeability will be measured including 12-24-h urinary sucralose (primarily representing colonic permeability)

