**Sample Size Analysis:** All power estimates were computed using R package pwr, and we assume a Type I error rate of 0.05 and a 2-sided test for all analyses. Power estimates were derived from the data from my prior K grant. The primary endpoints of this study will be phase angle/DLMO (Aim 1) and colonic permeability (13-24h urinary sucralose) (Aim 2). For Aim 1, we found a  $\sim 2$ h phase advance in DLMO in NW compared to DW at -0.2 (SD=2.1) compared to -4.34 (SD=3.8), respectively. With a sample size of 20 in each group (10 men/10 women), this

provides an 86% power to detect differences in DLMO, but 98% power if sex is pooled. For Aim 2, we found a 40% increase in colonic permeability in night shift workers compared to day workers after moderate alcohol consumption at 0.57 compared to 0.11 (SD=0.20). With 20 subjects, this will give us a 84% power to detect a difference in colonic permeability between the two groups for each sex and if sex is pooled will give us a 97% power with a two-sided two-sample t-test at alpha=0.05 level. These conservative estimates provide a good estimate of the power to detect differences in phase angle and colonic permeability between UC patients before and after simulated night shifts. We anticipate we will have nonparametric data and will use the Wilcoxon match-pair test for analysis of colonic permeability, inflammatory cytokines, and markers of endotoxemia. Order effects will be used as a covariate in multivariate analysis with analysis of variance (ANOVA) and linear regression as indicated. Microbiota data analysis is described above. Non-parametric analysis of actigraphy data will be analyzed with the nparACT package. In our periodogram analysis of time series data we will use Fast Fourier Transform Non-linear Least Squares (FFT-NLLS), a nonlinear least-squares algorithm of a times series typically used for luminescence data (149) and analyzed with Biodare software (150). Data will be presented as mean  $\pm$  SEM for variables that can be considered normally distributed (or median and range for variables not normally distributed). All analyses will use R (v.3.2.5), Biodare 2, and SPSS (SPSS Inc., Chicago, IL).

**Inclusion Criteria:** *Study will include individuals that are;*

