**Ulcerative Colitis:**

1. Patients with other forms of colitis such as Crohn's disease (CD) or indeterminate colitis
2. Patient with active UC (Mayo  $> 2$ )
3. Pancolonic UC (colitis past the splenic flexure, Montreal E3))
4. Gastrointestinal surgery
5. Other GI diseases or systemic diseases (cardiac, renal failure, cirrhosis)
6. Shift work in the last 6 months
7. Antibiotic use within last 12 weeks
8. Patients who have used anti-diarrheal agents such as Lomotil or Imodium within 3 days of the study
9. Prednisone use the last 30 days
10. Significant Depression (score  $\geq 14$  BDI)
11. Significant Anxiety (score  $\geq 40$  STAI)
12. Use of probiotic supplement in last 4 weeks except yogurt.
13. Intentional change in diet.

14. Chronic use of NSAIDS. A washout period of 3 weeks is needed before the subject could be enrolled into the study. Low dose aspirin is allowed.
15. Chronic Alcohol use. A washout period of 3 weeks is needed before the subject could be enrolled into the study.
16. Have children under 6 months

**Subject Recruitment:** All Human UC subjects will be recruited at the RUMC Digestive Disease Clinic and the Rush Crohn's and Colitis Center by the PI or Clinical Coordinator. Healthy control subjects will be recruited by established recruiting methods, which we have successfully used over the past ten years, including notices to local organizations and internet, newspaper, and radio advertising. Based on our experience, of the initial calls made by potential subjects, 15% remain interested in the study after they are informed of study procedures. Of these individuals, 70% pass an initial telephone screening (in which questions are asked about medical condition, current medication use and work and travel history). Of those remaining individuals, 33% pass the medical and psychological screening (described below), and of these, 70% complete the study.

In this study we will recruit 40 Human Subjects in the following two groups:

- 1) Ulcerative Colitis (UC) (n=20).
- 2) Healthy Controls (HC) (n=20).

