All experimental procedures will commence after admission to the CCC for a 7 day in-lab evaluation. The sleep episode will be the same as that maintained during the 2 weeks prior to the in-lab phase assessment. On Test Day 1 (TD1, Baseline alignment), at 0900h all subjects will have a unprepped flexible sigmoidoscopy (FS) with rectal biopsy collection (19 biopsies, ~15 cm from the anal verge), after which intestinal permeability will be assessed (24h urine collection after ingestion of a sugar cocktail: sucrose, mannitol, lactulose, sucralose103), and every 2 hour blood sampling during/surrounding standardized meals (primary and secondary outcomes for Specific Aims 1 & 2). During the last 8h of the phase assessment, subjects will be exposed to a background illumination ~3 lux to assess the endogenous circadian phase through hourly plasma melatonin (dim light melatonin onset, DLMO). On Protocol Day 3, subject behavioral cycles will be shifted by 12h, and this schedule will be maintained until Protocol Day 7. Following the short 4h sleep episode on Day 3, subjects will have 3 “night shift” days (Days 3-5). The 12h shift on Day 3 will be achieved by including an 8h wake episode and a 4h sleep opportunity, thereby maintaining the same sleep opportunity-to-wake ratio (1:2). The rationale for the 12h inversion of the sleep-wake timing is that we previously found that the influence of circadian misalignment on physiological variables are maximal when the sleep/wake and fasting/feeding cycle was shifted by ~12h relative to the endogenous circadian timing system. On Test Day 2 (TD2, Circadian misalignment), all subjects will have all the identical tests conducted as described on TD1; however, the FS and start of repeated measures will be at 2100 h – matched to the sleep/wake cycle and not clock time to isolate the impact of circadian misalignment. 24 hours prior to each flexible sigmoidoscopy, stool will be collected from subjects. Discharge from the lab will be on day 7 after an 8h sleep period. We will test for order effects (see Statistics).

**Blood draw.** Blood (30 cc) will be drawn in endotoxin free tube and serum then immediately separated and stored in -80°C freezer until measurement for Serum endotoxin (END). Blood will also be drawn for CBC, comprehensive biochemical profile [CMP that includes

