**Figure 1. Outcome Measures**

Aims	Outcome Measure	Test	Assessment	Statistical Test
Aim 1	Primary	Phase Angle of entrainment (DLMO – sleep onset)	Baseline	ANOVA
			Misalignment	
	Secondary	Clock gene expression in PBMCs	Baseline	Cosinor Analysis, Mixed Model ANOVA
			Misalignment	
Aim 2	Secondary	Urinary Melatonin	Baseline	Wilcoxon signed-rank test
			Misalignment	
	Exploratory	Clock gene expression and Per2::LUC in Colonic Organoids	Baseline	Cosinor Analysis, FFT-NLLS
			Misalignment	
Aim 2	Primary	Intestinal Permeability (i.e. 12-24 h Urinary Sucralfate)	Baseline	Mann-Whitney U test
			Misalignment	
	Secondary	Mayo Score (Endoscopy)	Baseline	Wilcoxon signed-rank test
			Misalignment	
	Secondary	Stool Calprotectin	Baseline	Wilcoxon signed-rank test
			Misalignment	
Aim 2	Secondary	Serum cytokines (IL-6, TNF- $\alpha$ )	Baseline	Repeated measures ANOVA
			Misalignment	
	Secondary	Fecal Microbiota	Baseline	Principal Coordinate Analysis
			Misalignment	
Aim 2	Secondary	Serum LBP, LPS, zonulin, sCD14, metabolomics	Baseline	Repeated measures ANOVA
			Misalignment	
	Exploratory	TER in 2D Colonic	Baseline	ANOVA

		Organoids with ex-vivo TNF- $\alpha$ /INF- $\gamma$	Misalignment	
Exploratory		RNA seq of Colonic Organoids	Baseline	JTK Cycle
			Misalignment	

**Safety and Adverse Events:** We have identified five key potential risks to human subjects in this study:

1. Risk to Confidentiality and Record-Keeping of patient personal health information (PHI).
2. Risk of potential side effects associated with Phlebotomy (blood draw).
3. Risk of potential side effects associated with Sigmoidoscopy and Colonic Biopsy.
4. Risk of potential side effects associated with completion of the Questionnaires.
5. Risk of potential side effects associated with in lab study

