3. **Minimize the risk of potential side effects associated with Sigmoidoscopy.** The primary risk for most subjects undergoing sigmoidoscopy and biopsy is minimal discomfort during sigmoidoscopic examination. Risks include discomfort from air being added into the colon, bloating much like gas pain, possible irritation and a small amount of blood loss. On extremely rare occasions (1 in 17,000), the procedure can cause a tear or hole in the lining of the colon or significant bleeding. This may require surgery to repair. The PI (GS), who will perform all sigmoidoscopic examinations, is an experienced gastroenterologist with extensive experience in endoscopy over the last 10+ years. He has never experienced any subject complications while performing thousands of sigmoidoscopies. Furthermore, these sigmoidoscopic examinations will be limited to the most distal 15 to 20cm of the rectum and sigmoid rather than the typical, routine examination that requires advancing the scope to 45 to 60 cm (this shorter advancement of the scope is adequate to determine whether there is active disease and to obtain biopsies). Thus, discomfort and risk will be markedly lower than routine testing. Thus, unlike in routine sigmoidoscopy, we will do the procedure without any colon preparation (eliminate discomfort associated with laxative) and to a more limited extent. This limited procedure is not associated with any significant discomfort (no need to negotiate colon flexures that is the main source of discomfort associated with endoscopic procedures) and significantly decreases (and in fact eliminates) the tiny risk of perforation (< 1/10,000) associated with routine sigmoidoscopy. This opinion is based on our lab's 30+ years of experience performing limited sigmoidoscopy in research subjects in our sections and also based on personal experience—the PI (GS) has been a "healthy control" subject in several prior studies and has undergone this limited sigmoidoscopy and biopsy. The biopsy procedure is routine and painless with a tiny risk (< 1/10,000) of significant bleeding. The PI has obtained pinch mucosal biopsy

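### The plan does not say who grades the Mayo Endoscopic Score or whether grading is masked, and it gives the score conflicting outcome status

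*Combined protocol and SAP*

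**What the plan says.** **Status of the score.** The Primary outcome measures list under Study Outcomes says, for Aim 2, "Mayo Endoscopic Score and Intestinal permeability will be measured". The Sample Size Analysis says "The primary endpoints of this study will be phase angle/DLMO (Aim 1) and colonic permeability (13-24h urinary sucralose) (Aim 2" and names no endoscopic score. Figure 1 (Outcome Measures) labels the endoscopic Mayo row Secondary and assigns it a Wilcoxon signed-rank test.

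**Who does what.** Minimizing Risk, item 3, describes the PI as the person "who will perform all sigmoidoscopic examinations" and calls the limited view "adequate to determine whether there is active disease and to obtain biopsies". UC subjects are recruited "by the PI or Clinical Coordinator" (Subject Recruitment). The PI also gives the screening physical examination (Subject Recruitment) and interviews subjects in both groups (Data Analysis Methods).

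**Timing.** Under Procedures, the baseline sigmoidoscopy on Test Day 1 (TD1) is at 0900 h. On Test Day 2 (TD2), after the simulated night shifts, "the FS and start of repeated measures will be at 2100 h". The order is the same for every subject.

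**Masking.** No section names the person who assigns the endoscopic score. None describes recorded images, a second reader, scoring in random order, or concealment of group or session. The coding of folders and specimens concerns storage.

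**The concern.** An endoscopic grade depends on the eye of the person grading. If the PI grades at the procedure, as the plan makes likely, then group, session and the earlier grade are all known at TD2. The Abstract states the expected direction: misalignment raises mucosal inflammation in UC. UC subjects enter with inactive disease (Mayo score of 2 or less), so there is more room to move up than down, and a handful of grade changes can settle a paired test. An apparent worsening on this score would then be hard to separate from what the grader expected to see.

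How much this matters depends partly on the score's status, which the plan gives in three incompatible ways.

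**Working it through.** The plan gives no effect size, SD or power for the endoscopic score, so there is no figure of its own to reproduce. The check asks how many upward gradings the planned test needs.

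**Inputs from the documents**
- 20 UC subjects (Subject Recruitment).
- Wilcoxon signed-rank test (Figure 1).
- Two-sided alpha of 0.05 (Sample Size Analysis).
- A past completion rate of 70% (Subject Recruitment).

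**Assumption.** Every non-zero change is one grade. All ranks then tie, and the exact signed-rank test equals the sign test. With u upgrades, d downgrades, m = u + d and u > d:

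p = 2 × Σ (j = 0 to d) C(m, j) / 2^m

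| Upgrades | Downgrades | Exact two-sided p |
|---|---|---|
| 5 | 0 | 2/32 = 0.0625 |
| 6 | 0 | 2/64 = 0.031 |
| 7 | 1 | 2 × (1 + 8)/256 = 0.070 |
| 8 | 1 | 2 × (1 + 9)/512 = 0.039 |

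Six upgrades in 20 is 30% of subjects, a mean shift of 6/20 = 0.30 grade. If 20 is the number enrolled and 70% complete, 0.70 × 20 = 14 pairs remain. Six upgrades are still needed, and 6/14 = 43%.

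**Asymptotic version.** The plan does not say which version will be used. Without continuity correction, z = (u − d)/√(u + d). Four upgrades and no downgrades give z = 4/2 = 2.0 and p = 0.046. Seven upgrades and one downgrade give z = 6/√8 = 2.12 and p = 0.034. With continuity correction, five upgrades and no downgrades give p = 0.037.

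**Chance of a significant worsening when nothing has changed.** Further assumptions, none from the documents: each subject is randomly misread by one grade with probability q in each direction (0 to 15%), plus an extra upward misreading with probability b at TD2. Summing the trinomial probabilities with n = 20, upgrade probability q + b and downgrade probability q, over all outcomes with u > d and p ≤ 0.05, gives the following. The asymptotic column uses no continuity correction.

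| Extra upward misreading b | Exact test | Asymptotic test |
|---|---|---|
| 0 | 0 to 0.6% | 0 to 2.4% |
| 10% | 1 to 5% | 9 to 15% |
| 20% | 15 to 20% | 22 to 59% |
| 30% | 31 to 58% | 40 to 89% |

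Ranges cover q from 0 to 15%. As a hand check, with q = 0 and b = 20% the exact figure is the chance that a binomial(20, 0.2) count is at least 6, which is 0.196.

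**The case against.** **The score may not be primary.** Two of the three places that rank Aim 2 outcomes do not make it so, and no power calculation rests on it. This stands. A reader of the outcome list alone might infer that a settled primary endpoint is at risk, but the documents do not support that until they are reconciled.

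**The scorer is inferred.** A reader might conclude that the plan has the PI grade live and unmasked. No section says so. Performing every procedure makes it likely, and the defect that can be shown is that the scorer and the masking are unspecified.

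**The bias needed is not slight.** A reader might infer that a small expectation effect would be enough. As a mean shift, 0.2 to 0.3 grade sounds modest, but it means a full-grade upgrade in 4 to 6 of 20 subjects with none lower. One downgrade raises the exact requirement to eight. At 10% extra misreading the exact test rarely gives a false result.

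**Other measures test the same hypothesis.** Urinary sucralose, stool calprotectin and the serum markers are laboratory assays, and this bias does not reach them. This stands too: a spurious endoscopic result would appear beside them, so the conclusion on inflammation does not rest on the score alone.

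**The between-group contrast.** The PI knows each subject's group, so bias there is possible. Figure 1 gives only a paired test for this score, and nothing in the documents allows the between-group effect to be sized.

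None of these points supplies a masking procedure, so the gap itself remains.

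**Conclusion.** The concern holds in limited form. The score's status is contradictory and must be reconciled. Under either label it is a subjective grade, with no stated scorer or masking, in a design where the endoscopist knows group and session. Expectation bias could contribute to an apparent worsening. It matters less if the score is secondary.

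The sizes in the working rest on assumed misreading rates and one-grade changes. They show what the planned test is sensitive to; they do not estimate how much bias would occur. Masked scoring would not separate misalignment from the fixed order of the two sessions, which is a different matter.

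**What to change.** 1. Give the Mayo Endoscopic Score one status, and state it consistently in Study Outcomes, Figure 1 and the Sample Size Analysis.
2. Name the scorer.
3. At each sigmoidoscopy already planned, save a short clip or a fixed set of stills before that session's biopsies. Take them from a segment away from the TD1 biopsy sites and drop any frame that shows them. TD1 takes 19 biopsies at about 15 cm and the examination covers only the distal 15 to 20 cm, so visible sites could reveal the TD2 session.
4. Have the coordinator store the files under a coded ID without group, date or time. After enrolment ends, or in batches, the PI scores all files in random order across groups and sessions.
5. Use the masked score in the analysis. Keep the live grade for clinical use and as a sensitivity analysis. State whether the signed-rank test is exact or asymptotic.

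**Cost.** A little coordinator and scoring time, with no added procedure, visit or reader. Some unprepped images will be harder to grade than the live view. Masking is partial, because the same PI may recognise a case. Images not saved at the procedure cannot be recovered, so the change should be made before further procedures take place.

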#### **Secondary outcome measures:**

- **Aim 1 – Circadian Misalignment of peripheral clocks:** Clock gene expression (CLOCK, BMAL) in PBMCs during each phase assessment and in colonic biopsies
- **Aim 2 – Barrier Function:** Colonic mucosal AJC proteins (E-cadherin, occludin, claudin2,3,4), stool calprotectin and mucosal and stool microbiota composition and function. Studies will include serum markers of intestinal permeability and bacterial translocation [lipopolysaccharide (LPS) and LPS-binding protein (LBP)]; serum zonulin and intestinal fatty acid protein; immune changes (serum interleukin-6 as proinflammatory marker and soluble CD14 as marker of macrophage/monocyte

activation); and stool and serum metabolomics: short-chain fatty acid (SCFA) and Trimethylamine N-oxide (TMAO) and TMA.

### Exploratory Outcome Measures:

- **Aim 1** – Colonic clock gene expression and Per2::Luc activity in colonic organoids over 24 hours in both groups and each condition
- **Aim 2** – RNA seq of colonic organoids every 2 hours for over 24 hours to identify key molecular and inflammatory pathways under circadian regulation
- **Aim 3**: Use body temperature to measure central circadian rhythm to see if it correlates with melatonin levels at baseline and after misalignment

**Figure 1. Outcome Measures**

Aims	Outcome Measure	Test	Assessment	Statistical Test
Aim 1	Primary	Phase Angle of entrainment (DLMO – sleep onset)	Baseline	ANOVA
			Misalignment	
	Secondary	Clock gene expression in PBMCs	Baseline	Cosinor Analysis, Mixed Model ANOVA
			Misalignment	
Aim 2	Secondary	Urinary Melatonin	Baseline	Wilcoxon signed-rank test
			Misalignment	
	Exploratory	Clock gene expression and Per2::LUC in Colonic Organoids	Baseline	Cosinor Analysis, FFT-NLLS
			Misalignment	
Aim 2	Primary	Intestinal Permeability (i.e. 12-24 h Urinary Sucralfate)	Baseline	Mann-Whitney U test
			Misalignment	
	Secondary	Mayo Score (Endoscopy)	Baseline	Wilcoxon signed-rank test
			Misalignment	
	Secondary	Stool Calprotectin	Baseline	Wilcoxon signed-rank test
			Misalignment	
Aim 2	Secondary	Serum cytokines (IL-6, TNF- $\alpha$ )	Baseline	Repeated measures ANOVA
			Misalignment	
	Secondary	Fecal Microbiota	Baseline	Principal Coordinate Analysis
			Misalignment	
Aim 2	Secondary	Serum LBP, LPS, zonulin, sCD14, metabolomics	Baseline	Repeated measures ANOVA
			Misalignment	
	Exploratory	TER in 2D Colonic	Baseline	ANOVA

		Organoids with ex-vivo TNF- $\alpha$ /INF- $\gamma$	Misalignment	
Exploratory		RNA seq of Colonic Organoids	Baseline	JTK Cycle
			Misalignment	

**Safety and Adverse Events:** We have identified five key potential risks to human subjects in this study:

1. Risk to Confidentiality and Record-Keeping of patient personal health information (PHI).
2. Risk of potential side effects associated with Phlebotomy (blood draw).
3. Risk of potential side effects associated with Sigmoidoscopy and Colonic Biopsy.
4. Risk of potential side effects associated with completion of the Questionnaires.
5. Risk of potential side effects associated with in lab study

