5. **Minimize the risk of potential side effects associated with in lab stay.** The subject may become sleepy during some segments of the study. The subject will be asked to remain awake during the entirety of their scheduled wake times. Should the subject feel that he/she is unable to remain awake, he/she is free to withdraw his/her consent to participate in this experiment and then go to sleep. At the end of the study, the subject may have difficulty sleeping and waking at their usual times. It may take several days to readjust to their regular routine. This experience is similar to jet lag, and may be associated with upset stomach, insomnia, irritability, or excessive daytime sleepiness. The protocol is designed so that changes in circadian phase are minimized. Subjects may not sleep as well in the laboratory as they do when at home. This may be exacerbated during the simulated night shift when subjects remain continuously awake. Nevertheless, short term partial sleep loss has never been shown to be directly deleterious to health although sleep loss can cause drowsiness and increase the risk of accidents. While dangerous accidents are unlikely in the controlled environment of the laboratory, we have less control when subjects leave the laboratory. Thus, we will ensure that the subject fully appreciates this risk and they will be given the opportunity

to have recovery sleep after completion of the protocol before leaving the laboratory. Taxi rides are arranged so that subjects can return home safely.

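### A before/after fall in urinary melatonin cannot by itself be attributed to the clock, and the paired test does not ask whether UC differs from controls

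*Combined protocol and SAP*

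**What the plan says.** In Figure 1 (Outcome Measures) the row "Urinary Melatonin" is a secondary outcome with two assessments, Baseline and Misalignment, and the test given is "Wilcoxon signed-rank test". The row shows no group comparison and no adjustment. It lies among the clock-gene rows, so it is read here as a clock outcome, although the table as extracted puts an Aim 2 label beside it.

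Procedures sets out the two test days:

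- Test Day 1 (TD1, baseline): "at 0900h all subjects will have a unprepped flexible sigmoidoscopy". On sleep timing: "The sleep episode will be the same as that maintained during the 2 weeks prior to the in-lab phase assessment".
- The shift, on Protocol Day 3: "subject behavioral cycles will be shifted by 12h, and this schedule will be maintained until Protocol Day 7".
- Test Day 2 (TD2, misalignment): the same tests, but "the FS and start of repeated measures will be at 2100 h", which follows the shifted sleep/wake cycle and not the clock.
- Light: "During the last 8h of the phase assessment, subjects will be exposed to a background illumination ~3 lux to assess the endogenous circadian phase", read from hourly plasma melatonin as DLMO. No other light level appears in the readable text.
- Urine: the only test-day collection described is the 24-hour one for the sugar test. No window or assay is given for urinary melatonin.

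Minimizing Risk, item 5, says that subjects stay awake throughout the simulated night shift, and adds: "The protocol is designed so that changes in circadian phase are minimized".

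**The concern.** Urinary melatonin over a day is an amount. If it comes from a 24-hour collection, each sample covers one full cycle, and the total says almost nothing about when secretion occurred. The plan means to hold phase nearly still, yet sleep state, and probably light, change across the hours in which melatonin is secreted. The plan itself uses dim light when it reads phase from plasma melatonin, and the urinary row states no equivalent.

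Two things are at stake. A significant fall, reported beside the clock-gene results, could be taken as evidence of clock disruption when the comparison cannot separate that from light or wakefulness. Second, Aim 1 asks whether misalignment is more common in UC than in controls and whether UC patients are more susceptible. Background A.5 motivates the melatonin question with a pilot in which two of four inactive IBD subjects secreted less than controls. Both are between-group questions, and a within-subject test answers neither.

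**Working it through.** The plan gives no effect size, standard deviation or power for urinary melatonin, so there is no figure to reproduce. The check is an overlap of clock times.

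**From the documents:** test days start at 0900 h (TD1) and 2100 h (TD2); sleep is habitual on TD1 and shifted by 12 h on TD2; ~3 lux applies for the last 8 h of the phase assessment.

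**Assumed:** 8 h of sleep starting at 2200, 2300 or 2400 h; a 10-hour biological night from 2 h before habitual sleep onset to habitual wake; no movement of the clock. The 8-hour dim window is read in two ways: (A) the last 8 h of the 24 h from the start of the test day; (B) the last 8 h of wake before sleep.

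**Example, sleep onset 2300 h.** The biological night is 2100–0700 h. Sleep is 2300–0700 h on TD1 and 1100–1900 h on TD2.

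- Reading A: dim light is 0100–0900 h on TD1 and 1300–2100 h on TD2. Hours asleep or dim within the night: 8 on TD1, 0 on TD2.
- Reading B: dim light is 1500–2300 h on TD1 and 0300–1100 h on TD2. Hours asleep or dim: 8 + 2 = 10 on TD1, and 4 (0300–0700 h) on TD2.

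With onset at 2200 or 2400 h, only reading A on TD2 changes: 1 h is dim at 2200 h onset.

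| Biological-night hours (of 10) | TD1 | TD2 |
|---|---|---|
| Asleep | 8 | 0 |
| Awake outside ~3 lux, reading A | 10 − 8 = 2 | 9 to 10 |
| Awake outside ~3 lux, reading B | 10 − 10 = 0 | 10 − 4 = 6 |

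**What this could do to the total.** Let *s* be the unknown proportion by which light in those hours suppresses secretion, and take secretion as flat over the 10 h (2300 h onset). Relative totals are:

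- Reading A: TD1 = 8 + 2(1 − s); TD2 = 10(1 − s)
- Reading B: TD1 = 10; TD2 = 4 + 6(1 − s)

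| s | Fall, A | Fall, B |
|---|---|---|
| 0 | 0% | 0% |
| 0.1 | 1 − 9/9.8 = 8% | 1 − 9.4/10 = 6% |
| 0.3 | 1 − 7/9.4 = 26% | 1 − 8.2/10 = 18% |
| 0.5 | 1 − 5/9 = 44% | 1 − 7/10 = 30% |
| 0.7 | 1 − 3/8.6 = 65% | 1 − 5.8/10 = 42% |

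For scale, use a paired t-test on the log ratio with n = 20, two-sided 0.05, and SD = √2 × CV, with an assumed within-subject CV of 0.30. Under reading B it would be significant in about 10%, 51% and 95% of trials at s = 0.1, 0.3 and 0.5, with no clock change. The result turns on *s*, which the readable text does not fix.

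**The case against.** A reader might infer that a fall reflects light suppression and not a change in the clock. The documents do not support that. The light level during the night shifts is not in the readable text, and a figure beside the in-lab procedures could not be read and may show it. Holding phase steady through a 12-hour inversion is at least as consistent with dim night shifts, in which case suppression could be small. An effect of the clock, sleep or posture is not excluded either.

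Other points on the plan's side:

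- The 24-hour urine window is inferred from the sugar test. This stands as a limit on the argument.
- Figure 1 lists both assessments for every row, so the layout names time points and not contrasts. UC and controls are matched, and a signed-rank test on matched pairs at each assessment is possible. It is the less likely reading: Sample Size Analysis speaks of UC patients before and after simulated night shifts, and Figure 1 uses a between-group test for permeability.
- The plan nowhere says that a fall will be read as clock disruption. Urinary melatonin is absent from the secondary list in Study Outcomes, and the central-clock primary is already phase angle from DLMO. This limits the stakes.
- Background A.2 includes light in its definition of misalignment, and A.4 links lower plasma melatonin to higher colonic permeability in night workers. Melatonin output under the shift is therefore a legitimate outcome, and treating it merely as a check of light exposure would go too far.
- Reading A puts the dim window after the assumed melatonin onset on TD1, which sits badly with its DLMO purpose. The more plausible reading B still leaves 6 against 0 hours.

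**Conclusion.** The point holds as one of attribution. The two test days differ in wake state, and probably in light, across the biological night: about 6 to 10 of 10 hours awake outside the ~3 lux window on TD2, against 0 to 2 on TD1, under the assumed sleep and secretion times. With phase change meant to be minimized, a before/after fall in a total amount cannot by itself be assigned to the clock. The paired test also leaves the UC-versus-control question unanswered.

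The size of any light suppression is not established; the percentages in the working are conditional illustrations. The verdict rests on reading the row as a within-subject comparison and on the urine being a 24-hour total. The phase-angle primary is unaffected. This is a cheap improvement to a secondary outcome.

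**What to change.** Change the urinary melatonin row in Figure 1 as follows.

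1. Compare UC with matched controls on the baseline (TD1) amount, with an analysis that respects the matching, for example a signed-rank test on UC-minus-control pair differences.
2. Compare the TD2-minus-TD1 change between UC and controls in the same way. This removes the light effect common to both groups. If suppression is proportional, use log amounts: with a common fraction f and baselines b(UC) and b(HC), raw changes differ by −f × [b(UC) − b(HC)], while both log changes equal ln(1 − f).
3. Keep the within-group change as a description of melatonin output under the shift condition, not as evidence of a clock change.
4. Draw central-clock conclusions from plasma DLMO at ~3 lux.
5. Name the urine collection that supplies the measurement.

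If the 24-hour urine is the source, this needs no new samples, only wording and analysis work. The price is that the within-group before/after result no longer counts as clock evidence. A UC-control difference in light response would also remain a possible explanation for a difference in change, and should be stated when that result is reported.
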